10.1.11. Publication Policy

• The results of this study may be published or presented at scientific meetings. If this is foreseen, the Investigator agrees to submit all manuscripts or abstracts to the Sponsor before submission. This allows the Sponsor to protect proprietary information and to provide comments.

- The Sponsor will comply with the requirements for publication of study results. In accordance with standard editorial and ethical practice, the Sponsor will generally support publication of multicenter studies only in their entirety and not as individual site data. In this case, a coordinating Investigator will be designated by mutual agreement.
- Authorship will be determined by mutual agreement and in line with International Committee of Medical Journal Editors authorship requirements.

10.2. Appendix 2: AEs and SAEs: Definitions and Procedures for Recording, Evaluating, Follow-up, and Reporting

10.2.1. **Definition of AE**

AE Definition

- An AE is any untoward medical occurrence in a clinical study participant, temporally associated with the use of study intervention, whether or not considered related to the study intervention.
- NOTE: An AE can therefore be any unfavorable and unintended sign (including an abnormal laboratory finding), symptom, or disease (new or exacerbated) temporally associated with the use of study intervention.

Definition of Unsolicited and Solicited AE

- An unsolicited AE is an AE that was not solicited using a participant diary and that is communicated by a participant who has signed the informed consent. Unsolicited AEs include SAEs and nonserious AEs.
- Potential unsolicited AEs may be medically attended (ie, symptoms or illnesses requiring a hospitalization, emergency room visit, or visit to/by a healthcare provider). The participants will be instructed to contact the site as soon as possible to report medically attended event(s), as well as any events that, though not medically attended, are of participant concern. Detailed information about reported unsolicited AEs will be collected by qualified site personnel and documented in the participant's records.
- Unsolicited AEs that are not medically attended nor perceived as a concern by the participant will be collected during an interview with the participants and by review of available medical records at the next visit.
- Solicited AEs are predefined local (at the injection site) and systemic events for which the participant is specifically questioned, and which are noted by the participant in their diary.

Events Meeting the AE Definition

- Any abnormal safety assessments (eg, vital signs measurements), including those that worsen from baseline, considered clinically significant in the medical and scientific judgment of the Investigator (ie, not related to progression of underlying disease, or more severe than expected for the participant's condition).
- Exacerbation of a chronic or intermittent pre-existing condition including either an increase in frequency and/or intensity of the condition.
- New condition detected or diagnosed after study intervention administration even though it may have been present before the start of the study.
- Signs, symptoms, or the clinical sequelae of a suspected drug-drug interaction.

• Signs, symptoms, or the clinical sequelae of a suspected overdose of either study intervention or a concomitant medication. Overdose per se will not be reported as an AE/SAE unless it is an intentional overdose taken with possible suicidal/self-harming intent. Such overdoses should be reported regardless of sequelae.

Events not Meeting the AE Definition

- Any abnormal findings or other abnormal safety assessments that are associated with the underlying disease, unless judged by the Investigator to be more severe than expected for the participant's condition.
- The disease/disorder being studied or expected progression, signs, or symptoms of the disease/disorder being studied, unless more severe than expected for the participant's condition.
- Medical or surgical procedure (eg, endoscopy, appendectomy): the condition that leads to the procedure is the AE.
- Situations in which an untoward medical occurrence did not occur (social and/or convenience admission to a hospital).
- Anticipated day-to-day fluctuations of pre-existing disease(s) or condition(s) present or detected at the start of the study that do not worsen.

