8.4.2. Method of Detecting AEs and SAEs

An eDiary has specifically been designed for this study by the Sponsor for collection of solicited ARs (see Section 8.3.3). At the time of consent, the participants must confirm they will be willing to complete the eDiary to record solicited ARs that occur during the 7 days following each vaccine administration (ie, the day of study intervention dosing and 6 subsequent days [Days 1-7 and Days 22-28]). The diary will include prelisted ARs (solicited ARs) and intensity scales.

At every in-person visit or telephone contact, participants will be asked a standard question to elicit any medically related changes in their well-being (including surveillance for respiratory viral infection symptoms) for detection of unsolicited AEs, according to the scripts provided. Participants will also be asked if they have been hospitalized, had any accidents, used any new medications, changed concomitant medication regimens (both prescription and OTC medications), or had any nonstudy vaccinations.

The Investigator is responsible for the documentation of AEs regardless of treatment group or suspected causal relationship to the study intervention. For all AEs, the Investigator must pursue and obtain information adequate to determine the outcome of the AE and to assess whether the AE meets the criteria for classification as an SAE or AESI requiring immediate notification to the Sponsor or its designated representative.

Care will be taken not to introduce bias when detecting AEs and/or SAEs. Open-ended and nonleading verbal questioning of the participant is the preferred method to inquire about AE occurrences.

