6.3.2. Adverse Events

An AE is any untoward medical occurrence in a clinical study participant, temporally associated with the use of study intervention, whether or not considered related to the study intervention. An AE can therefore be any unfavorable and unintended sign (including an abnormal laboratory finding), symptom, or disease (new or exacerbated) temporally associated with the use of study intervention. AEs will also be evaluated by the investigator for the coexistence of MAAE which is defined as an AE that leads to an unscheduled visit to a healthcare practitioner (HCP).

For analysis purpose, an AE is defined as any event occurring during the study but not present before exposure to study vaccine. Worsening of a pre-existing condition after vaccination will be reported as a new AE.

An unsolicited AE is any AE reported by the participant that is not specified as a solicited AR in the protocol or is specified as a solicited AR but starts outside the protocol-defined period for

reporting solicited ARs (i.e., 7 days after each study injection). For analysis and reporting purpose, unsolicited AEs will include the following:

- AEs that are reported by participants and recorded on the AE eCRF
- Solicited ARs that meet SAE criteria or last beyond 7 days after each injection and are recorded on the Reactogenicity eCRF

Unsolicited AEs will be collected for up to 21 days after each injection; SAEs, MAAEs, AESIs, and AEs leading to study discontinuation will be collected throughout the study. Unsolicited AEs will be summarized up to 21 days separately after Day 1 injection and Day 22 injection unless otherwise specified. Additionally, SAEs, MAAEs, AESIs and AEs leading to study discontinuation will be summarized throughout the study (up to Day 202/EoS). Refer to Safety Estimand 3b in Appendix G, Table 6.

All summary tables (except for the overall summary of AEs) for unsolicited AEs will be presented by SOC and PT (or by PT). SOC will be displayed in internationally agreed order. PTs will be displayed in descending order of frequency in the "D1: Fluzone HD+mRNA-1345 (pug) and D22: placebo" group and then alphabetically within SOC. When summarizing the number and percentage of participants with an event, participants with multiple occurrences of the same AE or a continuing AE will be counted once.

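### Protocol 10.2.1 excludes the disease under study from the AE definition, contradicting other AE provisions, so non-serious RSV or influenza illness could be recorded inconsistently

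*Protocol*

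**What the plan says.** Protocol 10.2.1 (Definition of AE) has a list of events that do not meet the definition. One bullet reads "The disease/disorder being studied or expected progression, signs, or symptoms of the disease/disorder being studied", and goes on to except illness worse than expected given the participant's condition. The disease is not named there or defined elsewhere.

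Four other provisions bear on the same events:

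- The general definition in 10.2.1 makes an AE of any unfavorable sign, "symptom, or disease (new or exacerbated) temporally associated with the use of study intervention".
- The list in 10.2.1 of events that do meet the definition includes a "New condition detected or diagnosed after study intervention administration".
- Protocol 8.4.2 has sites put a standard question at every visit or call, "including surveillance for respiratory viral infection symptoms", and gives its purpose as finding unsolicited AEs.
- SAP 6.3.2 states that, for analysis, "an AE is defined as any event occurring during the study but not present before exposure to study vaccine". It has no exclusion for the disease under study.

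Unsolicited AEs through 21 days after each injection, and MAAEs through Month 6 after the last injection, are primary safety endpoints (protocol Table 2; SAP 3.1.1).

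**The concern.** The bullet fits a treatment trial in patients who already have the disease, where its ordinary course should not be counted as an adverse event. Here participants are medically stable adults of 65 and over, vaccinated against RSV and influenza. If those are the diseases being studied, the bullet tells a site not to record a new, ordinary case of either, while other provisions tell the same site to record it.

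What is at stake is the completeness and consistency of the two endpoints at source. A MAAE must first be an AE (protocol 8.4.6 and 10.2.3), so whatever a site decides about the AE carries over to the MAAE. The objectives include no RSV or influenza case endpoint that would capture the illness in another way.

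**Working it through.** This is a question of text, and no figure in the plan depends on the bullet. The one safety figure given is the probability of about 95% of seeing at least one participant with an AE at a true rate of 0.3% among 950 per arm (protocol 9.3; SAP 4.3). It gives 1 − (1 − 0.003)^950 = 0.942, close to the stated value, and does not change under either reading.

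**Step 1: does the exception work?** It keeps illness that is worse than expected for the participant's condition. That needs a condition at entry to compare with. Inclusion criterion 2 requires medical stability, exclusion criterion 1 removes the acutely ill, and exclusion criterion 6 removes anyone with a positive influenza or RSV test in the 6 months before Day 1. A participant who falls ill with RSV after dosing had no such illness at entry, so the exception gives the site no usable threshold.

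**Step 2: apply each provision to one case.** Take a participant whose own doctor diagnoses uncomplicated influenza 10 days after the Day 1 injection, with no admission.

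| Provision | Is it an AE? |
|---|---|
| 10.2.1, general definition | Yes: a new disease after dosing |
| 10.2.1, new-condition bullet | Yes |
| 8.4.2, detection question | Yes: the symptoms are sought in order to find unsolicited AEs |
| SAP 6.3.2 | Yes: not present before exposure |
| 10.2.1, disease-under-study bullet | No, if influenza is taken as a disease being studied |

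If recorded, the case counts as an unsolicited AE and, because of the doctor's visit, as a MAAE. If the bullet is applied, it counts as neither.

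**Step 3: can the analysis repair an omission?** SAP section 1 says the SAP prevails where its methods differ from the protocol's. But SAP 6.3.2 builds unsolicited AEs from entries on the AE eCRF, plus certain solicited reactions from the Reactogenicity eCRF. An illness never entered is not there to be counted. Protocol 6.9.2 requires recording of medications used for RSV disease or other infectious symptoms, which leaves a trace of treatment but not an event record. SAP section 7 does not address the point.

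**Step 4: does the contradiction reach SAEs?** Protocol 10.2.2 defines an SAE through any untoward medical occurrence meeting a seriousness criterion, with no exclusion for the disease under study. An admitted, life-threatening or fatal case qualifies on that wording.

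**Step 5: size.** The documents give no rate of RSV or influenza illness. Purely as an assumption, rates of 0.5% to 5% over follow-up would mean 1900 × 0.005 = 9.5, or about 10, to 1900 × 0.05 = 95 participants whose illness is open to either reading. This is a ceiling on what could be affected, not an estimate of loss.

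**The case against.** The strongest reply is that most of the text points toward recording. The general definition, the new-condition bullet and the question put at every contact all do so, and 10.2.1 also asks participants to report medically attended illness. The bullet speaks of progression and of the participant's condition, and its neighbours concern underlying or pre-existing disease, so its natural subject is illness held at entry. The trial has no disease endpoint, so calling RSV and influenza the diseases being studied is itself an interpretation. This largely stands: it shows that omission is a possible reading, not an instruction running through the protocol. It does not remove a bullet that says the opposite and leaves its key term undefined.

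Further replies stand. The schedule includes no RSV or influenza testing, so the bullet would bite mainly where an outside provider had made the diagnosis. The eCRF, its completion guidelines and the call scripts are not among the documents, and they may already settle the matter.

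A reader might infer a bias between arms, because Arm 2 has no RSV vaccine until Day 22. The documents do not support this. That interval is 21 of the 201 days from Day 1 to Day 202. Staff assessing participants are blinded, so differing site practice is not in itself related to arm. Interference between the vaccines is judged on titers and response rates, not on illness counts.

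**Conclusion.** The contradiction is real and lies in current protocol text. If a site applies the bullet, non-serious RSV or influenza illness drops out of unsolicited AEs and MAAEs, and the analysis cannot restore it. How many events this would affect is unknown.

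Two stronger readings go too far. One is that the protocol definitely removes these illnesses from the safety endpoints; several provisions direct sites to record them, so the supported conclusion is possible inconsistency. The other is that SAEs are lost. Section 10.2.1 does place SAEs among unsolicited AEs, and 8.4.2 has the investigator judge whether an AE is serious, but the SAE definition's own wording covers any case meeting a seriousness criterion.

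The conclusion assumes that some sites would take RSV or influenza as the disease being studied, and that no operational document outside the protocol and SAP already says otherwise. No sample size, power figure or immunogenicity hypothesis is affected.

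**What to change.** Delete the bullet from protocol 10.2.1. Alternatively, replace it with a statement that RSV, influenza and other respiratory illness with onset after dosing is recorded as an AE, and also as a MAAE or SAE when those criteria are met. Put the same rule in the eCRF completion guidelines so that they agree with protocol 8.4.2 and SAP 6.3.2.

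The cost is a change to one bullet, matching site guidance and slightly more AE entries. No visit, procedure or analysis is added.

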10.2.2. Definition of SAE

An SAE is defined as any untoward medical occurrence that, at any dose, meets one or more of the criteria listed:

a. Results in death

b. Is life-threatening

The term *life-threatening* in the definition of *serious* refers to an event in which the participant was at risk of death at the time of the event. It does not refer to an event, which hypothetically might have caused death, if it were more severe.

c. Requires inpatient hospitalization or prolongation of existing hospitalization

- In general, hospitalization signifies that the participant has been admitted (usually involving at least an overnight stay) at the hospital or emergency ward for observation and/or treatment that would not have been appropriate in the physician's office or outpatient setting. Complications that occur during hospitalization are AEs. If a complication prolongs hospitalization or fulfills any other serious criteria, the event is serious. When in doubt as to whether hospitalization occurred or was necessary, the AE should be considered serious.
- Hospitalization for elective treatment of a pre-existing condition that did not worsen from baseline is not considered an AE.

d. Results in persistent or significant disability/incapacity

• The term disability means a substantial disruption of a person's ability to conduct normal life functions.

• This definition is not intended to include experiences of relatively minor medical significance such as uncomplicated headache, nausea, vomiting, diarrhea, influenza, and accidental trauma (eg, sprained ankle) that may interfere with or prevent everyday life functions but do not constitute a substantial disruption.

e. Is a congenital anomaly/birth defect

f. Other situations:

- Medical or scientific judgment should be exercised by the Investigator in deciding
 whether SAE reporting is appropriate in other situations such as important medical
 events that that may not be immediately life-threatening or result in death or
 hospitalization but may jeopardize the participant or may require medical or surgical
 intervention to prevent one of the other outcomes listed in the above definition. These
 events should usually be considered serious.
 - Examples of such events include invasive or malignant cancers, intensive treatment in an emergency room or at home for allergic bronchospasm, blood dyscrasias, convulsions not resulting in hospitalization, or development of intervention dependency or intervention abuse.

10.2.3. Definition of MAAE

A MAAE is an AE that leads to an USV to a healthcare practitioner. This would include visits to a study site for unscheduled assessments not required per protocol (e.g., rash assessment, abnormal laboratory follow-up) and visits to healthcare practitioners external to the study site (e.g., emergency room, urgent care, primary care physician).

10.2.4. Definition of AESI

An AESI is an AE (serious or nonserious) of scientific and medical concern specific to the Sponsor's product or program, for which ongoing monitoring and immediate notification by the Investigator to the Sponsor are required. Such events may require further investigation to characterize and understand them.

The AESIs defined for this protocol can be found in Section 10.3.1.

10.2.5. Recording and Follow-Up of AE and/or SAE

AE and SAE Recording

- When an AE/SAE occurs, it is the responsibility of the Investigator to review all documentation (eg, hospital progress notes, laboratory reports, and diagnostics reports) related to the event.
- The Investigator will then record all relevant AE/SAE information.
- It is not acceptable for the Investigator to send photocopies of the participant's medical records to the Sponsor or designee in lieu of completion of the eCRF /required form.
- There may be instances when copies of medical records for certain cases are requested by the Sponsor or designee. In this case, all participant identifiers, with the

exception of the participant number, will be redacted on the copies of the medical records before submission to the Sponsor or designee.

• The Investigator will attempt to establish a diagnosis of the event based on signs, symptoms, and/or other clinical information. Whenever possible, the diagnosis (not the individual signs/symptoms) will be documented as the AE/SAE.

Assessment of Intensity

The Investigator will make an assessment of intensity for each AE and SAE reported during the study and assign it to one of the following categories:

Mild

A type of AE that is usually transient and may require only minimal treatment or therapeutic intervention. The event does not generally interfere with usual activities of daily living.

Moderate

A type of AE that is usually alleviated with additional specific therapeutic intervention. The event interferes with usual activities of daily living, causing discomfort but poses no significant or permanent risk of harm to the research participant.

Severe

A type of AE that interrupts usual activities of daily living, or significantly affects clinical status, or may require intensive therapeutic intervention.

The Toxicity Grading Scale for Healthy Adult and Adolescent Volunteers Enrolled in Preventive Vaccine Clinical Trials (DHHS 2007) will be used to categorize local and systemic reactogenicity events (solicited ARs), clinical laboratory test results, and vital sign measurements observed during this study. The intensity grading scale used in this study is presented in Table 7.

Table 7: Adult and Adolescent Solicited Adverse Reactions and Grades

Reaction	Grade 0 (None)	Grade 1 (Mild)	Grade 2 (Moderate)	Grade 3 (Severe)	Grade 4 (Life-threatening)
Local					
Injection site pain	None	No interference with activity	Some interference with activity	Prevents daily activity	Requires emergency room visit or hospitalization
Injection site erythema (redness)	<25 mm/ <2.5 cm	25-50 mm/ 2.5-5 cm	51-100 mm/ 5.1-10 cm	>100 mm/ >10 cm	Necrosis or exfoliative dermatitis
Injection site swelling/induration (hardness)	<25 mm/ <2.5 cm	25-50 mm/ 2.5-5 cm	51-100 mm/ 5.1-10 cm	>100 mm/ >10 cm	Necrosis

Reaction	Grade 0 (None)	Grade 1 (Mild)	Grade 2 (Moderate)	Grade 3 (Severe)	Grade 4 (Life-threatening)
Axillary (underarm) swelling or tenderness ipsilateral to the side of injection	None	No interference with activity	Some interference with activity	Prevents daily activity	Requires emergency room visit or hospitalization
Systemic					
Headache	None	No interference with activity	Some interference with activity	Prevents daily activity	Requires emergency room visit or hospitalization
Fatigue	None	No interference with activity	Some interference with activity	Prevents daily activity	Requires emergency room visit or hospitalization
Myalgia (muscle aches all over body)	None	No interference with activity	Some interference with activity	Prevents daily activity	Requires emergency room visit or hospitalization
Arthralgia (joint aches in several joints)	None	No interference with activity	Some interference with activity	Prevents daily activity	Requires emergency room visit or hospitalization
Nausea/vomiting	None	No interference with activity or 1-2 episodes/ 24 hours	Some interference with activity or >2 episodes/24 hours	Prevents daily activity, requires outpatient intravenous hydration	Requires emergency room visit or hospitalization for hypotensive shock
Chills	None	No interference with activity	Some interference with activity not requiring medical intervention	Prevents daily activity and requires medical intervention	Requires emergency room visit or hospitalization
Fever (oral)	<38.0°C <100.4°F	38.0-38.4°C 100.4-101.1°F	38.5-38.9°C 101.2-102.0°F	39.0-40.0°C 102.1- 104.0°F	>40.0°C >104.0°F

Note: Events listed above but starting >7 days poststudy intervention dosing will be recorded in the eCRF. Causality for each event will be determined per assessment by the Investigator.

Modified from the Toxicity Grading Scale for Healthy Adult and Adolescent Volunteers Enrolled in Preventive Vaccine Clinical Trials (DHHS 2007).

Assessment of Causality

- The Investigator is obligated to assess the relationship between study intervention and each occurrence of each AE/SAE. The Investigator will use clinical judgment to determine the relationship.
- Not related: There is not a reasonable possibility of a relationship to the study intervention. Participant did not receive the study intervention OR temporal sequence of the AE onset relative to administration of the study intervention is not reasonable OR the AE is more likely explained by another cause than the study intervention.
- Related: There is a reasonable possibility of a relationship to the study intervention. There is evidence of exposure to the study intervention. The temporal sequence of the AE onset relative to the administration of the study intervention is reasonable. The AE is more likely explained by the study intervention than by another cause.
- For causality assessment, the Investigator will also consult the IB and/or product information, for marketed products.
- The Investigator must review and provide an assessment of causality for each AE/SAE and document this in the medical notes. There may be situations in which an SAE has occurred and the Investigator has minimal information to include in the initial report to the Sponsor or designee. However, it is very important that the Investigator always make an assessment of causality for every event before the initial transmission of the SAE data to the Sponsor or designee.
- The Investigator may change their opinion of causality in light of follow-up information and send an SAE follow-up report with the updated causality assessment.
- The causality assessment is one of the criteria used when determining regulatory reporting requirements.

Follow-up of AEs and SAEs

- The Investigator is obligated to perform or arrange for the conduct of supplemental measurements and/or evaluations as medically indicated or as requested by the Sponsor or designee to elucidate the nature and/or causality of the AE or SAE as fully as possible. This may include additional laboratory tests or investigations, histopathological examinations, or consultation with other health care professionals.
- If a participant dies during participation in the study or during a recognized follow-up period, the Investigator will provide the Sponsor or designee with a copy of any postmortem findings including histopathology.
- New or updated information will be recorded in the originally submitted documents.
- The Investigator will submit any updated SAE data to the Sponsor or designee within 24 hours of receipt of the information.

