6.3.1. Solicited Adverse Reactions

An AR is any AE for which there is a reasonable possibility that the test product caused the AE. The term "Solicited Adverse Reactions" refers to selected signs and symptoms occurring after each injection administration during a specified post-injection follow-up period (day of injection and 6 subsequent days). The solicited ARs are recorded by the participant in eDiary. The eDiary will solicit daily participant reporting of ARs using a structured checklist (Section 8.3.3 of the study protocol). Participants will record such occurrences in an eDiary from Day 1 through Day 7 (i.e., the day of injection and 6 subsequent days). Local solicited ARs will be recorded separately for each injection site (left and right arm). Severity grading of reactogenicity will occur automatically based on participant entry in the eDiary according to the grading scales presented in Table 7 of the study protocol, which are modified from the toxicity grading scale for healthy adult and adolescent volunteers enrolled in preventive vaccine clinical trials (DHHS 2007). All solicited ARs (local and systemic) reported in the eDiary will be considered causally related to study injection.

If a participant had a Grade 1 or higher AR during the solicited period and did not record the event in the eDiary, the event should be recorded on the Reactogenicity eCRF. If the event starts during the solicited period, but continues beyond 7 days after dosing, the participants should notify the site to provide an end date and close out the event on the Reactogenicity eCRF. If the participant reported an event that started after the solicited period (i.e., beyond 7 days after

dosing), it should be recorded as an AE on the AE eCRF. Causality for these events will be determined per assessment by the Investigator.

The following local ARs for each injection site (left and right arm) will be solicited by the eDiary: injection site pain, injection site erythema (redness), injection site swelling/induration (hardness), and axillary (underarm) swelling or tenderness ipsilateral to the injection arm. The following systemic ARs will be solicited by the eDiary: headache, fatigue, myalgia (muscle aches all over the body), arthralgia (aches in several joints), nausea/vomiting, chills, and fever.

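### Protocol 10.2.5 applies two incompatible causality tests: an AE with a reasonable possibility of vaccine causation but a likelier alternative is coded *Not related*, and a tie fits neither category

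*Protocol*

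**What the plan says.** The causality part of Protocol 10.2.5 gives the investigator a two-level scale.

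- The upper level opens: "Related: There is a reasonable possibility of a relationship to the study intervention". Sentences on exposure and on timing follow, and the last sentence is "The AE is more likely explained by the study intervention than by another cause".
- The lower level opens: "Not related: There is not a reasonable possibility of a relationship to the study intervention". It then lists three conditions joined by OR: no receipt of the intervention, an unreasonable time sequence, and finally "OR the AE is more likely explained by another cause than the study intervention".

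The section also says "The Investigator will use clinical judgment to determine the relationship". It requires a causality call on every event before an SAE is first transmitted, even when little is known, and it names causality among the inputs to regulatory reporting decisions.

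SAP 6.3.1 introduces adverse reactions with reasonable possibility alone: "An AR is any AE for which there is a reasonable possibility that the test product caused the AE". The SAP gives no separate rule for the word treatment-related. SAP 6.3.2.1, 6.3.2.2 and 6.3.2.4 tabulate treatment-related events by treatment group, among them unsolicited AEs, SAEs, MAAEs and severe AEs.

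**The concern.** Reasonable possibility and likelier than any other cause are different thresholds. An event can pass the first and fail the second. The scale is headed by the first, but its detailed conditions apply the second.

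The events most exposed are those with a ready competing explanation. Protocol 5.1 admits adults aged 65 or older with chronic diagnoses, provided they are medically stable. Protocol 10.2.1 counts worsening of a pre-existing condition as an AE. Reactions of a solicited type that start after the 7-day diary period also come under investigator causality (Protocol 8.4.5).

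At stake are the treatment-related tables and one element of the expedited-reporting decision, since Protocol 8.4.4 turns on suspected unexpected serious adverse reactions.

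**Working it through.** The plan gives no figure on this point, so there is none to reproduce. The check is logical: run every type of event through both definitions.

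**Inputs (Protocol 10.2.5).** Exposure: yes or no. Timing reasonable: yes or no. Relative likelihood: vaccine likelier, equal, or other cause likelier. That gives 2 × 2 × 3 = 12 combinations.

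**Rules.**
- *Related* = exposed AND timing reasonable AND vaccine likelier.
- *Not related* = not exposed OR timing unreasonable OR other cause likelier.

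The protocol prints no AND between the *Related* sentences. I read them as joint conditions because they mirror, one by one, the OR list under *Not related*.

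**Results.**

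| Combination | Count | Category |
|---|---|---|
| Not exposed (any timing, any likelihood) | 1 × 2 × 3 = 6 | Not related |
| Exposed, timing unreasonable | 1 × 1 × 3 = 3 | Not related |
| Exposed, timing reasonable, other cause likelier | 1 | Not related |
| Exposed, timing reasonable, equally likely | 1 | Neither |
| Exposed, timing reasonable, vaccine likelier | 1 | Related |

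Totals: *Related* 1, *Not related* 6 + 3 + 1 = 10, neither 1, sum 12.

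**The two problem rows.**
- *Other cause likelier.* If a vaccine contribution is still reasonably possible, the event satisfies "There is a reasonable possibility of a relationship to the study intervention", the headline of *Related*. It also satisfies "the AE is more likely explained by another cause than the study intervention", which suffices for *Not related*. The event takes the second label while contradicting that label's opening sentence.
- *Tie.* The event fails the comparative sentence of *Related* and triggers none of the three conditions for *Not related*. A causality call is nevertheless compulsory, so the site must choose without a rule.

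**Alternative reading.** If the *Related* sentences are not joint conditions, an event with a likelier alternative can meet both categories at once. The text then overlaps instead of excluding, and it still needs correcting.

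**Size.** If p is the proportion of participants with a related event under reasonable possibility, and s is the share of them whose only such events have a likelier alternative, the reported proportion is p × (1 − s). Neither p nor s is in the documents, so I attach no number.

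**The case against.** The strongest reply is that each opening sentence states the concept and the later sentences say how to apply it, with clinical judgment governing throughout. On that reading only the tie is a gap, and preferring a more inclusive threshold is a matter of taste. Part of this stands: judgment does govern, and a tie is unclassified, not lost, since an investigator may well code it *Related*. But the likelier-alternative condition is explicit and sufficient on its own. Judgment applied through it gives *Not related* however reasonable the possibility.

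Four stronger readings are tempting, and the documents do not support them.

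- *Detection of a coadministration signal is weakened.* The primary safety endpoints (Protocol Section 3, SAP 3.1.1) and Safety Estimand 3b (SAP Appendix G) do not depend on the investigator's causality call. AEs are documented whatever their suspected cause (Protocol 8.4.2). All-causality tables by arm are planned by SOC and PT, SMQ and HLGT. Suspected myocarditis and pericarditis go to a blinded adjudication committee (SAP 6.3.2.7). No hypothesis uses related-AE counts.
- *The arms are biased against each other.* One scale serves both arms, and investigators are blinded apart from the unblinding that Protocol 6.4.1 permits. Nothing shows a differential effect.
- *Serious events could be held back.* All SAEs reach the sponsor within 24 hours with no causality filter (Protocol 8.4.1), and AESIs need immediate notification (Protocol 10.2.4). Only the later, causality-based reporting step is touched.
- *The SAP contradicts the protocol outright.* The SAP 6.3.1 sentence introduces solicited ARs, which are related by rule, and does not define treatment-related for unsolicited AEs. It shows a different wording of the standard, not two rules feeding one table.

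**Conclusion.** The point holds in a limited form. Protocol 10.2.5 contradicts its own headline standard for events with a likelier alternative cause and leaves ties without a category. The consequence is possible under-counting in the treatment-related tables for investigator-assessed events, and an effect on one input to expedited reporting. All-causality results, the primary safety endpoints, solicited ARs and SAE notification to the sponsor stand as planned.

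The conclusion assumes that investigators apply the printed conditions and that the *Related* sentences are joint. If the second assumption fails, the defect becomes an overlap. The direction for likelier-alternative events is toward fewer related events. For ties it depends on what each site does. The size is unknown.

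**What to change.** In Protocol 10.2.5:

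1. Make reasonable possibility, as judged by the investigator, the single governing test for both categories.
2. Keep exposure, timing and alternative causes as factors to weigh, not as separate conditions.
3. State that a likelier alternative does not by itself make an AE *Not related* if a reasonable possibility remains.
4. Assign ties to *Related*.

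*Related* should not be reduced to exposure plus plausible timing. Unsolicited AEs are collected for 21 days after each injection in dosed participants, so most could then qualify, and the related tables would approach the all-causality ones.

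Carry the same text into the eCRF completion guidelines. The cost is wording only: visits, samples, sample size and hypotheses do not change. Related-AE counts would rise somewhat and become less specific. The SAP cannot recover calls already made under the present text, so the report should say which wording applied to them.
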